7.4 Safety Analysis Population for DIAN-TU-001 Subjects

The safety analysis population includes all subjects who have consented to participate and have received at least one dose of any study drug or placebo. Subjects in the safety analysis population will be allocated into treatment arms "as treated" in the event that randomized treatment is incorrectly dispensed and continues to be the treatment during the follow-up. Subjects in the safety analysis population will be allocated into treatment arms "as initially treated" in the event that a subject incidentally receives a dose or multiple doses of an incorrect treatment but receives the correct treatment for the other doses; this subject's treatment

assignment will not be changed because of the incorrectly administered dose. For any study drug, this population includes the mutation positive subjects on the active treatment, mutation positive subjects on placebo (including the direct placebos, and the concurrently randomized placebos), and mutation negative subjects on placebo (including only the direct placebos and concurrently randomized placebos).

7.5 Modified Intent-to-Treat (mITT) Analysis Population for DIAN-TU-001 Subjects

The mITT analysis population includes all randomized subjects who receive any treatment post-randomization and have at least one assessment for any one of the four tests contributing to DIAN-MCE at baseline and at least one post-baseline assessment for the same test that is either during treatment or no later than 56 days post-treatment. Subjects in the mITT analysis population will be allocated into treatment arms "as randomized".

7.6 Per-Protocol (PP) Population for DIAN-TU-001 Subjects

The PP population includes all subjects in the mITT analysis population who do not have any major protocol violations. The important protocol violations will be defined for each study drug respectively before locking the clinical database and prior to unblinding the trial. The PP analysis population will be considered the supportive analysis population for the primary endpoint, for selected sensitivity analyses, and for selected secondary endpoints.

7.7 Analysis Population for Primary/Secondary/Exploratory Analyses

The primary/secondary analysis population will include the mITT population and the eligible DIAN-OBS subjects, or the PP population and the eligible DIAN-OBS subjects. The mITT population and the eligible DIAN-OBS subjects will be used for all the efficacy endpoint analyses that uses data from DIAN-OBS subjects, including the primary, secondary, and biomarker endpoints and for all the subgroup analyses unless specified otherwise. The combined population of the PP population and the eligible DIAN-OBS subjects will be used as the supportive analysis population for analyses that use data from DIAN-OBS subjects within all primary and selected sensitivity and secondary endpoints.

8 GENERAL ISSUES FOR STATISTICAL ANALYSES

8.1 General Considerations

All statistical analyses and summary information are to be generated according to this SAP. Any deviations from this SAP will be documented in the CSR.

For continuous variables, descriptive statistics such as the number of patients (n), mean, standard deviation (SD) or standard error (SE), minimum, median, and maximum values will be reported. Lower and upper quartiles will be presented for select summaries. For categorical variables, frequencies and percentages will be displayed. Subject data collected in the electronic case report form (eCRF) and other data sources will be presented in listings.

All analyses, summary tables, figures, and data listings will be generated with SAS[®] version 9.1 or higher, or R, or with analysis code that has been appropriately validated such as FORTRAN codes for the MDPM.

Baseline dates are defined as the first treatment administration dates for subjects treated in DIAN-TU-001; for eligible DIAN-OBS subjects, the first DIAN-OBS visit dates where they became eligible will serve as the baseline dates. For DIAN-OBS run-in subjects, depending on which group they belong to (e.g., DIAN-TU-001 vs DIAN-OBS), the corresponding baseline dates will be used.

Baseline is defined as the latest non-missing DIAN-TU-001 measurement taken prior to study drug administration. For blood pressure, baseline will further be defined as the latest time prior to study drug administration where both systolic and diastolic blood pressure measurements are available. Baseline will not be defined for subjects who never took the study drug. For assessments collected without a time measurement on the date of the first dose, the assessment can contribute to baseline if it was scheduled per protocol to take place prior to dosing.

Summaries by visit will be based on the nominal visit. Early discontinuation assessments of efficacy will be included at the annual visit when it occurs +/- 6 months relative to the visit, except in cases where a scheduled visit was conducted for the corresponding annual visit. Unscheduled visits will not contribute to by-visit analyses.

The clinical/cognitive tests contributing to DIAN-MCE collected more than one visit or more than 56 days (i.e., two visit intervals) after drug discontinuation will not be included in the primary or secondary analysis.

8.2 Type I Error Rate Control

The primary analysis for each study drug is based on a Bayesian posterior probability. This posterior probability of slowing the rate of cognitive decline is used to determine success on the primary efficacy analysis. The posterior probability threshold is selected to control the type I error rate for the multivariate analysis of DIAN-MCE. The type I error rate is the probability of rejecting the null hypothesis that there is no difference in cognitive decline or there is faster decline in the subjects in the active drug arm compared to those in the pooled control group with dynamic borrowing when the null hypothesis is true.

Although this study investigates multiple study drugs with shared placebos for the primary efficacy analysis, no adjustment for multiple drugs will be done. Each drug is considered to have its individual 2.5% type I error rate.

There will be no comparison between study drug arms.

For any secondary analyses based on the MDPM or UDPM, the test will be one-sided with a type I error rate of 0.025 for each analysis. For any secondary analyses based on the linear mixed effects (LME) model or the mixed-effects model for repeated measures (MMRM) or any other frequentist models, the test will be two-sided with a type I error rate of 0.05 for each analysis.

8.3 By-Center Analyses and Pooling of Sites

This platform study is conducted in three regions, USA/Australia/Canada, Europe, and the rest of the world. This study is being conducted at approximately 30 global sites. The homogeneity of treatment effects across investigational sites will be investigated using descriptive statistics.

8.4 Handling of Missing Values

The primary analysis uses all observed data. There is no preliminary step of imputation for missing data, and the results obtained in this way are consistent with the missing at random assumption for all missing data. The sensitivity analyses to evaluate the effect of the missing-at-random

assumption are provided in Section D of [12.1.6.7](#). If subjects remained in the trial following drug discontinuation, the endpoints collected after drug discontinuation (only for drug discontinuation described in Protocol Section 4.4.1) will not be included in the primary, secondary and sensitivity analyses.

The clinical/cognitive tests contributing to DIAN-MCE collected more than one visit or more than 56 days (i.e., two visit intervals) after drug discontinuation will not be included in the primary analysis or secondary analysis.

Similarly, the clinical/cognitive tests contributing to secondary endpoints collected more than one visit or more than 56 days (i.e., two visit intervals) after drug discontinuation will not be included in the analysis.

8.5 Missing Values in the Questionnaires Contributing to Efficacy Endpoints

Missing values in the questionnaires (such as MMSE, Geriatric Depression Scale [GDS], Functional Assessment Scale [FAS], et al.) are expected to be rare. If at any given visit, the number of missing items within a questionnaire is less than 30% of the total number of items, then the score for this component at this visit will be calculated as the sum of the non-missing items multiplied by the ratio of the total number of items to the number of the non-missing items [6]. If the number of missing items is equal to or greater than 30%, then the score at this visit is considered missing [6].

Values captured within the FAS as ‘not applicable (e.g., never did)’ (NA) will be treated as missing.

8.6 Re-Randomization

As described in SAP [Section 3.1](#), mutation negative subjects are assigned to a placebo arm. If a subject’s mutation status is misclassified prior to randomization, i.e., a mutation positive subject is misclassified as mutation negative, the subject will be re-randomized as a mutation positive subject.

The date of re-randomization will be used as the randomization date for the re-randomized subjects. Any data collected prior to the re-randomization date will be considered as belonging to the subject's screening or baseline assessments based on when the data are collected. For the subject who is re-randomized, any adverse events (AEs) and/or serious adverse events (SAEs) that occurred prior to the re-randomization will be treated as medical history, although they may appear in listings that include events which started prior to treatment. The re-randomized subjects will be identified in the CSR.

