3 STUDY METHODS

3.1 Overall Study Design

This trial is a Phase II/III double-blind, placebo-controlled study of potential disease modifying therapies in individuals with or at risk for dominantly inherited Alzheimer's disease. This trial will have two arms for each study drug, the active study drug and the blinded placebo for that study drug. Subjects will be recruited from various sources, i.e., participating DIAN-observational (DIAN-OBS) study sites, DIAN-TU-001 trial sites, DIAN-TU-001 partner sites, the DIAN Expanded Registry study, and families identified by the sites.

Mutation positive subjects who signed the informed consent form (ICF), met eligibility requirements and completed all baseline evaluations will be randomized in a 3:1 ratio to receive either the active study drug or placebo for the active study drug. Mutation negative subjects will be assigned only to the placebo arm. If two or more placebo arms are enrolling simultaneously, mutation negative subjects will be equally randomized to these placebo arms. Mutation negative subjects will not be included in the efficacy/futility analyses. Data from mutation negative subjects will be evaluated for safety and used to develop models for longitudinal changes in biomarkers and cognition in healthy adult controls.

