13.1 Duration of Treatment

Duration of treatment (days) will be defined for each subject as

- Duration of treatment (days) = date of last dose – date of first dose +1.

Duration of treatment summarized as total days per patient will be presented by treatment using the descriptive statistics including mean (SD), 25th percentile, median, and 75th percentile.

The proportion and frequencies of incomplete infusions will be summarized by doses and compared between treatment arms.

The total number of administered doses (including both fully and partially administered) for each subject will be summarized by treatment arms and by dose levels within each active treatment arm using descriptive statistics.

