13.2 Adverse Events

An AE is defined as any untoward medical occurrence in a clinical trial subject, whether it is considered to be drug related. AEs will be recorded and assessed as to whether they are treatment-emergent adverse events (TEAEs). TEAEs are defined as events that first occur or worsen (increase in severity) after the first dose of the study drug. The onset date/time of an AE will be compared to the date/time of first dose of the study drug to determine if the AE is treatment emergent or not. If the AE onset date is missing or partial, the date will be compared as far as possible with the date of first dose of the study drug. AEs will be assumed to be treatment-emergent unless there is clear evidence (through comparison of partial dates and/or collected assessment of

whether the AE started prior to the first dose of the study drug) suggesting the AE started prior to the first dose of study medication.

An overall summary of TEAEs will be presented with the number and percentage of subjects having a TEAE, a severe TEAE, a TEAE related to study treatment, a serious TEAE, a TEAE leading to study discontinuation, and a TEAE with an outcome of death. The overall summary will be presented for each study drug arm, the mutation positive placebo arm, and the mutation negative placebo arm. The summary will also be reported by doses (low (the initial dose) vs high (escalated doses) at the time of initiation of the high dose). The number of TEAEs per patient-year of exposure will also be presented, where patient years will be the sum of treatment duration in a column converted to years.

All TEAEs will be summarized by the *Medical Dictionary for Regulatory Activities* (MedDRA) System Organ Class (SOC) and Preferred Term (PT). The dictionary version will be established and documented during the blinded data review meeting prior to lock of the data.

Subjects experiencing more than one TEAE by SOC and PT will only be counted once at the preferred terminology level in AE frequency tables, but each unique TEAE will be included in the total number of TEAEs (where provided) for each SOC and PT. The overall summary for SOC and PT will be presented for each study drug arm, the mutation positive placebo arm, and the mutation negative placebo arm. The summary will also be reported by doses (low (the initial dose) vs high (escalated doses) at the time of initiation of the high dose).

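### For re-randomized subjects, SAP 8.6 turns AEs and SAEs that follow a blinded placebo dose into medical history, against 13.2 and 7.4, and no section says which first dose then governs

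*SAP*

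**What the plan says.** Section 8.6 covers one kind of error: "a mutation positive subject is misclassified as mutation negative, the subject will be re-randomized as a mutation positive subject". Until the error is found, such a subject is handled as mutation negative, and Section 3.1 states: "Mutation negative subjects will be assigned only to the placebo arm". Any dosing before re-randomization is therefore blinded placebo.

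For the time before re-randomization, 8.6 makes three provisions:

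- The re-randomization date becomes the randomization date.
- On data, the sentence that opens "Any data collected prior to the re-randomization date will be considered as belonging to the" goes on to place such data with screening or baseline, depending on timing.
- On safety, the rule is "any adverse events (AEs) and/or serious adverse events (SAEs) that occurred prior to the re-randomization will be treated as medical history". A closing clause then leaves listing of these events optional: "although they may appear in listings that include events which started prior to treatment".

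It also requires these subjects to be identified in the CSR.

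The general definitions have no exception for these subjects:

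- Section 13.2: "TEAEs are defined as events that first occur or worsen (increase in severity) after the first dose of the study drug".
- Section 13.1: "Duration of treatment (days) = date of last dose – date of first dose +1". Section 13.2 uses the sum of these durations in a column as the denominator of the TEAE rate.
- Section 8.1: "Baseline dates are defined as the first treatment administration dates for subjects treated in DIAN-TU-001".
- Section 7.4 admits a subject to the safety population after one dose of drug or placebo.

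**The concern.** An AE or SAE in someone who has already received blinded trial product is an on-treatment event, even when the product was placebo given after a genotyping error. Calling it medical history removes it from the counts that the safety section is there to produce. The affected outputs are the TEAE summaries and the serious-TEAE line of the overall summary. What remains is optional appearance in a listing of events that preceded treatment, and that label is wrong for a subject who had been dosed.

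The time origin is a second gap. TEAE status, treatment duration and baseline date all depend on the first dose, and a re-randomized subject who was already dosed has two candidates for it. A programmer applying 8.1, 8.6, 13.1 and 13.2 to that subject must choose one, and the plan does not record the choice.

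**Working it through.** The SAP gives no count of re-randomized subjects and no rate on this point, so there is no figure to reproduce. The check has two parts: following the rule through the definitions, and a scale calculation on stated assumptions.

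**Which events the rule changes.** Section 3.4 places randomization at the baseline visit, before the first dose. Under 13.2, an event that starts before any dose, and does not worsen afterwards, is not a TEAE. For a subject never dosed before re-randomization, 8.6 therefore changes nothing in the TEAE tables. It changes them only for events after a placebo dose.

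**The two readings of first dose.**

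- *Original placebo dose.* By 13.2 the events are TEAEs, but 8.6 makes them medical history. By 13.1 the placebo time stays in treatment duration. The numerator loses the events while the denominator keeps the time. Under 8.1 the baseline date is the first placebo dose, yet 8.6 assigns data collected after that dose to screening or baseline.
- *First dose after re-randomization.* 8.6, 13.1 and 13.2 now agree, and events and time drop out together. But a dosing period in a subject who already met 7.4 then contributes neither events nor exposure to any summary.

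Neither reading reports the placebo-period events in a summary table.

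**Scale, first reading only.** Inputs:

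- Column sizes: 52 active and 34 pooled mutation positive placebo (Gantenerumab appendix, Section 3.4).
- Follow-up: 48 months, the minimum in Section 3.6, used as 4 years per subject.
- Assumed, not in the SAP: 1 to 3 re-randomized subjects in the column, each with 1 to 24 months of earlier placebo dosing.

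Proportional fall in the column rate = extra PY / (PY + extra PY), where PY is patient-years and extra PY is the earlier dosing time counted without its events.

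- Column PY: 52 × 4 = 208; 34 × 4 = 136.
- Smallest extra PY: 1 × 1/12 = 0.083. Largest: 3 × 24/12 = 6.
- Active column: 0.083 / 208.083 = 0.04%, up to 6 / 214 = 2.8%.
- Pooled placebo column: 0.083 / 136.083 = 0.06%, up to 6 / 142 = 4.2%.

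Under the second reading this mismatch is zero.

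**The case against.** The strongest defence is that 8.6 is the specific rule and resets the clock. It moves the randomization date, sends earlier data to screening or baseline, and describes the earlier events as preceding treatment. Read this way, the first dose in 13.1 and 13.2 is the one after re-randomization, and nothing is mismatched. The rule is openly declared, the subjects are named in the CSR, and there may be few of them or none who had been dosed.

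Much of this stands. A reader might infer that the placebo dosing time stays in exposure. The SAP does not say so: that follows only from a literal reading of 13.1, and the wording of 8.6 supports a reset at least as well. A reader might also infer that the SAEs vanish from the SAE listing. That does not follow either, because 13.2 does not restrict that listing to TEAEs and 8.6 allows listing, although it does not guarantee it. Nor does 8.6 state a rival baseline date. It moves the randomization date and leaves the baseline date unaddressed.

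Prior dosing is not proved by the mention of AEs, since AEs can occur before any dose.

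The defence does not answer the central point. A reset makes the sections consistent by leaving a blinded dosing period and its SAEs out of every summary. Naming the subjects in the CSR does not put the events back or tell the programmer which first dose to use.

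**Conclusion.** The point holds as a conflict in the rule together with an unstated time origin. As written, 8.6 disagrees with the TEAE definition in 13.2 and does not fit the safety population in 7.4. For a subject dosed before re-randomization, it removes on-placebo AEs and SAEs from the TEAE and serious-TEAE summaries under either reading of first dose.

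The size is unknown and probably small. The column-rate range of 0.04% to 4.2% depends on the assumed 1 to 3 subjects and 1 to 24 months, and applies only if exposure is not reset. Two larger-looking measures should not be used:

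- The earlier placebo months as a share of one subject's total duration. The SAP plans no per-subject rate.
- One lost SAE as 1/34 of the pooled placebo column. The subject is re-randomized 3:1 to active, so is more likely to end up in an active column.

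The change is still worth making, because a pre-specified rule should not relabel serious events on blinded treatment as history, however few there are.

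**What to change.** Amend 8.6 for any re-randomized subject who had already been dosed:

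1. The first dose after re-randomization is the start date for baseline, treatment duration and TEAE assignment in the re-randomized arm. Cross-refer to this from 8.1, 13.1 and 13.2.
2. AEs and SAEs from the first placebo dose until that date are reported as on-placebo events with the exposure of the same period, either in a named placebo column or in a separate table. The column must be named because 13.2 has separate mutation positive and mutation negative placebo columns.
3. SAEs from that period *will*, not *may*, be in the SAE listing.

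The cost is SAP wording and one extra derivation rule. A few subjects would contribute to two displays, so 7.4, which allocates subjects to treatment arms, needs a stated exception. A separate table would leave the main columns unchanged.

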9 STUDY SUBJECTS

The following summaries and analyses will be conducted for the safety population for DIAN-TU-001 for data collected at DIAN-TU-001 visits unless specified otherwise.

9.1 Disposition of Subjects

The following subject data will be summarized for each study drug:

- Number of mutation positive subjects and mutation negative subjects by treatment and overall.
- Number of subjects randomized by region, by treatment and overall.
- Number of subjects at each visit by treatment.
- Number and percentage of subjects in each analysis population by treatment.
- Number and percentage of subjects who completed the study by treatment.
- Number and percentage of subjects who prematurely discontinued the study as well as number and percentage of subjects for each discontinuation reason.

In addition, subject listings will be provided for subjects who discontinue the study prematurely, or who are excluded from each analysis population (with reason for exclusion).

9.2 Protocol Violations

A summary will be provided to identify subjects who had important protocol violation(s) and a list will be provided for important protocol violation(s). The identification of the important protocol violation(s) will be discussed at the blind data review meeting.

9.3 Inclusion/Exclusion Criteria Violations

An appendix listing will be provided to identify subjects who were enrolled even though they did not meet one or more eligibility criteria.

10 DEMOGRAPHICS, BASELINE CLINICAL CHARACTERISTICS, AND FAMILY HISTORY

Descriptive safety summary outputs will be split in the following groups: the mutation negative direct placebo group, mutation positive placebo group, mutation positive direct placebo group, and the active treatment group.

Demographics and family history in dementia summary outputs will be split in the following groups: the DIAN-OBS subjects, mutation positive placebo group, and the active treatment group. DIAN-OBS subjects will be summarized for components that are collected in the same manner in both studies (DIAN-OBS and DIAN-TU-001). For DIAN-OBS run-in subjects, their demographics and family history, except where time dependent (e.g., age, EYO, baseline scores), will be based on DIAN-TU-001 data when summarizing the DIAN-OBS group.

